4.8 Criteria for Early Termination of the study

The short-term nature of the intervention and follow-up makes it unlikely that any new information will be of relevance to an individual participant. As far as we are aware, there are no similar studies recruiting obstetric participants. In the unlikely event that the cell salvage machine manufacturers (with whom we have good links) issue an important safety notice, we will suspend recruitment to the trial. Additionally, if the DMC committee, TSC, REC or sponsor determine it is within the best interests of the participants or trial to terminate the study, written notification will be given to the CI. This may be due to, but not limited to; safety concerns, proof of efficacy or non-compliance/serious breaches. If the study is terminated participants will be returned to the NHS normal follow up and routine care for IOCS and CS procedures.

4.9 End of Study Definition

When the last enrolled participant has been discharged from hospital, the REC will be notified of the trial completion. The final study report will be completed 6 months after the trial completion.

5

Laboratories (if applicable)

5.1 Central/Local Laboratories

NHS pathology services will conduct all study laboratory analysis.

5.2 Sample Collection/Labelling/Logging

Sample collection requirements include full blood count (FBC) for analysis of haemoglobin levels at both pre and post-operative time points. A Kleihauer test is also required to measure maternal exposure to fetal blood postoperatively. The requirement for anti-D will be determined by analysis of maternal and fetal blood types and rhesus status postoperatively. These tests are considered to be standard care for women undergoing caesarean section and do not constitute additional tests for trial purposes. Samples will be collected, labelled and processed according to NHS standard practice and logged onto the NHS database.

5.3 Sample Receipt/Chain of Custody/Accountability

Samples will be checked by laboratory staff as per NHS standard practice prior to processing. Any inconsistencies will be referred back to the person collecting the sample or the research team. All samples received and processed will be logged onto the NHS database.

5.4 Sample Analysis Procedures

Sample analysis will be conducted according to the NHS standard operating procedures.

5.5 Sample Storage Procedures (if applicable)

All samples will be processed upon receipt. No sample storage is required.

5.6 Data Recording/Reporting

Pathology reports will be printed and filed in the participants medical records as per usual NHS practice. The haemoglobin and Kleihauer results will then be transcribed to the trial CRF by a delegated member of the trial team. The CRF will be pseudonymised with all participant identifiers removed.

6.1 General Definitions

6.1.1 Adverse Event (AE)

An AE is any untoward medical occurrence in a participant receiving trial intervention, including occurrences which are not necessarily caused by or related to that intervention. An AE can therefore be any unfavourable and unintended sign (including an abnormal laboratory finding), symptom or disease temporarily associated with study activities.

6.1.2 Serious Adverse Event (SAE)

An SAE fulfils at least one of the following criteria in the context of the SALVO trial:

- Is fatal – results in death (NOTE: death is an outcome, not an event)
- Is life-threatening
- Requires prolongation of hospitalisation after CS beyond 7 nights.
- Results in persistent or significant disability/incapacity
- Is a congenital anomaly/birth defect
- Is otherwise considered medically significant by the Investigator

6.2 Investigators Assessment

6.2.1 Seriousness

The local Principal Investigator is responsible for the care of the participant, or in his absence an authorised medic within the research team, is responsible for assessing whether the event is serious according to the definitions given in section 6.1.

6.2.2 Causality

The Investigator must assess the causality of all serious adverse events in relation to the trial treatment according to the definition given

6.2.3 Expectedness

The investigator must assess the expectedness of all SAEs according to the definition given. If the SAE is unexpected and related, then it needs immediate reporting.

6.2.4 Severity

The Investigator must assess the severity of the event according to the following terms and assessments. The intensity of an event should not be confused with the term “serious” which is a regulatory definition based on patient/event outcome criteria.

Mild: Some discomfort noted but without disruption of daily life

Moderate: Discomfort enough to affect/reduce normal activity

Severe: Complete inability to perform daily activities and lead a normal life

6.3 Notification and reporting Adverse Events or Reactions

If the AE is not defined as SERIOUS, the AE is documented in the participants' medical notes (where appropriate) and the trial AE log and the participant is followed up by the research team.

6.4 Notification and Reporting of Serious Adverse Events

All SAEs occurring during the trial observed by the investigator or reported by the participant, whether or not attributed to the trial, will be documented in the participants' medical notes (where appropriate) and reported on the AE log for the trial. All SAEs will be followed up until resolution or the event is considered stable. The investigator may be asked to provide follow-up information. All related SAEs that result in a participant's withdrawal from the trial or are present at the end of the trial, should be followed up until a satisfactory resolution occurs.

A maximum hospital stay following CS is considered to be 7 days. Any stay longer than 7 days should be considered prolongation of existing hospitalisation and recorded as an SAE on the AE log.

Local Principal Investigators are responsible for reporting SAEs to the chief investigator and their host institution, according to local regulations. All SAE's are to be reported to the CI within 24 hours of learning of the event. The CI must then report SAE's that are considered to be 'related' and 'unexpected' to the PCTU QA manager and to the sponsor within the 24 hours and then to the Main REC within 15 days in line with the required timeframe and sponsor and PCTU SOPs. For further guidance on this matter, please refer to Appendix 1.

6.4.1 Expected Adverse Events

Although no serious adverse events are anticipated, it is possible that these may occur.

Risks related to trial procedures include;

- Maternal exposure to fetal blood,
- Amniotic fluid embolism and
- Severe hypotension
- Transfusion reaction,

These are considered low level risks that are unlikely to occur with increased frequency for trial participants. Should they occur with severity meeting the criteria for a serious adverse event, they will be reported as a related and unexpected SAE.

6.5 Urgent Safety Measures

The CI may take urgent safety measures to ensure the safety and protection of the clinical trial participants from any immediate hazard to their health and safety, in accordance with Regulation 30. The measures should be taken immediately. In this instance, the approval of the Licensing Authority Approval prior to implementing these safety measures is not required. However, it is the responsibility of the CI to inform the sponsor and MREC (via telephone) of this event immediately.

The CI has an obligation to inform the MREC in writing within 3 days, in the form of a substantial amendment. The sponsor (JRO) and PCTU QA manager must be sent a copy of the correspondence with regards to this matter. For further guidance on this matter, please refer to Appendix 2

6.6 Annual Safety Reporting

The CI will send the Annual Progress Report to the MREC using the NRES template (the anniversary date is the date on the MREC “favourable opinion” letter from the MREC) and to the sponsor. Please see Appendix 2 for further information. The CI will report a cumulative line listing of all related and unexpected SAEs to the MREC annually, and to the DMC and Trial Steering Committee every 6-12 months. The DMC will view data with knowledge of treatment. If a participant dies as a result of the study protocol or study interventions, any post-mortem findings must be provided to the Chief Investigator, who will report the findings to the DMC for continuous safety review.

6.7 Overview of the Safety Reporting Process/Pharmacovigilance responsibilities

The CI has the overall pharmacovigilance oversight responsibility. The CI has a duty to ensure that pharmacovigilance monitoring and reporting is conducted in accordance with the sponsor’s requirements and the PCTU SOP. An organogram of the communication of SAEs is shown in [Appendix 1](#). Each participating trial site will be responsible for reporting all SAEs to the chief investigator immediately so that a decision can be made as to whether this needs to be reported to the sponsor, PCTU QA manager and MREC. The CI will keep a log of all SAE’s reported by the participating centres for reporting to the REC and DMC.

7

Statistical Considerations

7.1 Trial Outcomes

7.1.1 Primary outcome

The primary outcome is the proportion of women needing donor blood transfusion to deal with haemorrhage and its consequences. (see section 3.5).

7.1.2 Secondary outcomes

- Severity of events quantified as the volume of blood transfused
- Time to first mobilisation after CS
- Length of hospital stay
- Multidimensional Fatigue Inventory (MFI)
- Resources used intra- and post-operatively, including IOCS consumables and donor blood transfusions
- Costs of staff training, service procurement and provision of care will be collected alongside clinical outcomes

7.1.3 Safety outcomes

- Pre- and post-operative serum haemoglobin, and mean fall in haemoglobin level
- Maternal exposure to fetal blood measured by Kleihauer test
- Requirement for and the dose of anti-D antibody administered

7.1.4 Process outcomes

- Volume of blood returned in IOCS (mean/SD)
- Proportion of transfusion reaction associated with allogeneic donor blood transfusion
- Episodes of technical failure of IOCS

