The use of leukocyte depletion filters in the return of salvaged blood has been the subject of scrutiny in the medical literature. There are some reports of unexplained hypotension associated with blood return and filters have been implicated as a potential source of anaphalactoid response. Whilst inclusion of a filter is currently recommended, they may restrict rapid re-infusion of blood in the context of massive haemorrhage and are routinely omitted at the discretion of clinicians when rapid blood return is imperative. We will monitor any reports of severe, unanticipated hypotension and their potential association with the presence of leukocyte filters to inform this on-going debate.

Risks associated with donor blood transfusion include death from transfusion error, acute transfusion reaction, fatal lung injury and infection transmission.

It is not anticipated that there be any additional pain, discomfort, distress, inconvenience or changes to lifestyle for research participants receiving IOCS compared to the standard care group. It is not anticipated that there will be any potential for adverse events, risks or hazards, pain, discomfort, distress, or inconvenience to the researchers themselves.

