4.7 Table 3: Schedule of Assessment

	Pre-operative	Intra- operative	Post-operative (24 hours)	Discharge
SCREENING				
Eligibility	X			
Informed consent	X			
Obstetric History/Prognostic Factors/ Indication CS/Demographics	X X			
Randomisation	X			
TRANSFUSION				
Transfusion of ≥ 1 unit donor blood		X	X	
Number of donor blood units transfused		X	X	
Volume of blood returned by IOCS		X		
IOCS consumables used		X		
IOCS technical failure		X		
MATERNAL				
Haemoglobin level	X		X	
Maternal exposure to fetal blood (Kleihauer test)			X	
Transfusion reaction			X	
Anti D requirement and dose			X	
Time to first mobilisation after CS			X	
Multidimensional Fatigue Inventory (MFI)				X
HEALTHCARE UTILISATION				
Length of hospital stay				X
Adverse Events		X	X	X

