7.4 Safety Endpoints

Adverse events will be recorded from the time of randomisation to the time of discharge. Safety outcomes will be compared between the groups, as for secondary endpoints.

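### The only named transfusion-reaction outcome counts reactions to donor blood and sits outside the safety outcomes compared between arms, so no all-source comparison of reactions is specified

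*Protocol*

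**What the plan says.** Protocol section 7.1.4 (Process outcomes) contains the only outcome that mentions transfusion reactions: "Proportion of transfusion reaction associated with allogeneic donor blood transfusion". It stands beside the volume of blood returned and technical failures of IOCS. No denominator is given.

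Section 7.1.3 lists the safety outcomes: haemoglobin, "Maternal exposure to fetal blood measured by Kleihauer test", and anti-D requirement and dose. Neither a transfusion reaction nor hypotension is among them. Section 7.4 then states: "Safety outcomes will be compared between the groups, as for secondary endpoints". It gives no such commitment for process outcomes.

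Elsewhere the protocol treats reactions more broadly:

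- Section 1.3.1 reports unexplained hypotension when salvaged blood is returned, says that "filters have been implicated as a potential source of anaphalactoid response", and undertakes to monitor severe hypotension and any link with the filters.
- Section 6.4.1, under "Risks related to trial procedures include", lists both severe hypotension and transfusion reaction.
- The schedule of assessment (4.7, Table 3) and the CRF list (8.3) carry the item "Transfusion reaction" without restricting it to donor blood.
- Section 4.6 says salvaged blood is returned to every woman in the IOCS arm whose collected volume is sufficient.

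**The concern.** Return of salvaged blood is the new exposure that the IOCS arm receives. A reaction outcome restricted to donor blood omits the reactions this exposure could cause and counts only those that IOCS is expected to reduce. The definition in 7.1.4 is also narrower than the data item in 4.7 and 8.3, so the outcome and the collected data do not match.

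This matters because the protocol treats fewer reactions as a benefit. Section 1.3.2 expects fewer transfusion reactions with IOCS, and 3.5 justifies the primary outcome partly by fewer transfusion-related complications. A count of one blood source cannot test that expectation for the IOCS policy as a whole. A report that followed the listed outcomes could show fewer reactions with IOCS even if the total across both sources were equal or higher.

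**Working it through.** **Inputs from the protocol.** 1,525 women per arm; donor transfusion 5% (control) and 3% (IOCS), relative risk 0.6 (7.5). Blood was returned in 16 of 22 women who had IOCS in the survey (1.3.7), and 16/22 = 72.7%.

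**Assumptions, because the protocol gives no reaction rates.** Let r be the reaction risk per donor-transfused woman (0.5% to 5%), s the reaction risk per re-infused woman, and q the share of the IOCS arm who have blood returned (30% and 50% assumed; 72.7% from the survey). IOCS use in the control arm is ignored, since 4.6 expects it to be very rare. Reactions from the two sources are added.

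**The plan's own figure.** The protocol states no figure for reactions, so the only figure to reproduce is the sample size that fixes the rates above. For 5% v 3%, two-sided 5%, 80% power and pooled variance:

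n = [1.960 × √(2 × 0.04 × 0.96) + 0.842 × √(0.0475 + 0.0291)]² / 0.02² ≈ 1,506 per arm, or 3,012 in total.

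This matches the table in 7.5. With the 1.2% allowance, 3,012/0.988 = 3,049, against 3,050 stated.

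**Step 1: donor-only count per randomised woman.** Expected women given donor blood: control 1,525 × 0.05 = 76.25; IOCS 1,525 × 0.03 = 45.75. Expected donor reactions are 76.25r and 45.75r, and the ratio is 45.75/76.25 = 0.6 for every r. The term s does not appear, so the ratio is the same whatever salvaged blood does.

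| r (assumed) | Control | IOCS | Probability that IOCS has more donor reactions (Poisson) |
|---|---|---|---|
| 0.5% | 0.38 | 0.23 | 15% |
| 1% | 0.76 | 0.46 | 20% |
| 2% | 1.53 | 0.92 | 23% |
| 5% | 3.81 | 2.29 | 20% |

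**Step 2: donor-only count per donor-transfused woman.** The risk is r in both arms, so the expected ratio is 1. This describes donor blood, not the IOCS policy.

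**Step 3: all-source count per randomised woman.** Control is 0.05r; IOCS is 0.03r + q·s. They are equal when s = 0.02r/q.

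- q = 72.7%: 1,525 × 16/22 = 1,109 re-infused; 30.5/1,109 = 0.0275, so s = 2.75% of r.
- q = 50%: 762.5 re-infused; 30.5/762.5 = 0.040, so s = 4% of r.
- q = 30%: 457.5 re-infused; 30.5/457.5 = 0.067, so s = 6.7% of r.

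Check at r = 2% and q = 72.7%: s = 0.0275 × 2% = 0.055%. IOCS total = 0.915 + 1,109 × 0.00055 = 1.525, equal to the control total of 1.525.

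**The case against.** The strongest reply is that reactions to salvaged blood are recorded. The schedule and CRF item is unrestricted. Section 7.4 states: "Adverse events will be recorded from the time of randomisation to the time of discharge". On the listed procedural risks, 6.4.1 adds: "Should they occur with severity meeting the criteria for a serious adverse event, they will be reported as a related and unexpected SAE". Under 6.6 related and unexpected SAEs go to a DMC that sees treatment allocation, and 10.6 lets the DMC ask for further analyses. Section 1.3.1 promises monitoring of severe hypotension, and 6.4.1 regards these risks as low and unlikely to be more frequent in participants. A process outcome may also be meant only descriptively, and an analysis plan not at hand could add a tabulation by arm and blood source.

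Most of this stands. A reader might infer from 7.1.4 that reactions to salvaged blood go unrecorded or can never be compared. The documents do not support that: the data are collected in both arms and the comparison is possible.

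A reader might also infer that the donor-only count can only favour IOCS. That is too strong as well. The 0.6 is an expectation, women in the IOCS arm also receive donor blood, and chance alone would put more donor reactions in that arm in about 15% to 23% of trials over the assumed range. The tilt also needs all randomised women as the denominator, which 7.1.4 does not state. Its wording could even mean the share of all reactions that were linked to donor blood.

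What the reply does not remove is the definition itself. The cumulative listing in 6.6 covers only related and unexpected SAEs, and 6.3 sends non-serious events to the notes and the AE log. Neither is a named outcome compared between arms. The protocol itself fixes what the outcome counts and where it is filed, so this is more than detail left to an analysis plan.

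**Conclusion.** The point holds as a gap in outcome definition, not in data capture. The sole named reaction outcome leaves out reactions to the blood that IOCS returns and lies outside the set that 7.4 compares between arms. Neither natural denominator gives a fair harm comparison: one carries a built-in expected ratio of 0.6, the other is uninformative about the policy.

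The 0.6 follows directly from the planning rates in 7.5. The break-even of 2.75% to 6.7% of the donor risk is illustrative only: it rests on a return share from 22 women who had IOCS for anticipated haemorrhage at one centre, or on assumed shares, and the documents do not show whether salvaged blood reaches that risk. Expected events are few on any of these assumptions. The primary outcome, its analysis and the sample size are unaffected. This should be fixed, but it does not threaten the main result.

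**What to change.** Add to 7.1.3 a safety outcome: any transfusion reaction, to donor or to returned salvaged blood, with all women randomised to each arm as the denominator, compared by arm under 7.4. Keep the donor-only item as a descriptive split of that outcome by blood source, and state its denominator. Record the blood source on the existing CRF item if it is not already there.

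The cost is one added and one reworded outcome and at most one tick-box. It needs no extra participants, visits or tests and no change in sample size. The drawback is that the comparison will rest on few events, so it should be reported as an estimate with its confidence interval, and a non-significant difference should not be read as evidence of equal safety.

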7.2 Primary Analysis

A detailed analysis plan will be developed and agreed by the Trial Steering Committee and the Data Monitoring Committee, prior to unblinding and data analysis. The primary analysis will be a comparison of the management policies assigned at randomisation (intention-to-treat). The risk of the primary outcome in the IOCS group will be compared with the usual practice group and tested for significance at the two-sided 5% level of significance. Crude and adjusted odds ratios and 95% confidence intervals will be produced (The adjusted analysis will be considered the primary analysis).

The analysis will be adjusted, to allow for known or suspected prognostic factors, to be specified in the analysis plan. Results will be reported according to the Gantt chart, Section 9.4.1.

The following subgroup analyses have been pre-specified for the primary outcome:

- analysis of treatment effect by indication for Caesarean Section.
- analysis of treatment effect by recruitment Centre.

The consistency of the treatment effect across subgroups will be explored using the statistical test of interaction. Further exploratory analyses will also be undertaken after the main trial report is complete. These will include an exploration of whether there are specific prognostic factors for intervention benefit or adverse outcomes, using tests of interaction. These analyses will be hypothesis-generating and the findings will be interpreted cautiously.

As a sensitivity analysis, we will analyse the primary outcome assuming that all instances of the use of IOCS in the control arm would have been instances of donor blood transfusion had the IOCS machine not been present.

7.3 Secondary Analysis

Analysis of secondary outcomes will be clearly delineated from the primary analysis in any statistical reports produced. Estimates of treatment effect (unadjusted, and adjusted for the same covariates as in the primary analysis) will be obtained using methods appropriate to the scale of measurement of the outcome (see Section 7.5). Analyses will be intention-to-treat.

[figure not shown]
7.4 Safety Endpoints

Adverse events will be recorded from the time of randomisation to the time of discharge. Safety outcomes will be compared between the groups, as for secondary endpoints.

7.5 Sample Size

The proposed sample size is a total of 3,050 women (1,525 per group). To detect an absolute difference of 2% in the transfusion rate as defined in Section 7.1.1 (5% in the standard care group, 3% in the IOCS group, relative risk 0.6) this sample size would give 80% power for a 2-sided test (Figure 6). In reaching this estimate we have considered definition of primary outcome, control event rate, expected effect size, choice of study design, power and directionality of hypothesis.

Figure 6: Power Curves

Establishing a baseline rate for the primary outcome is not straight forward since estimates in the published literature for blood transfusion in CS vary widely (1.8% to 23.5%) (2;3). Factors influencing this figure include country of origin, indication for CS and local transfusion policy. Contemporary observational reports put transfusion rates for an unselected CS population at around 5% in current UK practice. Our audit in two investigating centres has shown around a 5% transfusion rate. Our pilot sample is too small to assist in providing reliable information on sample size calculations. In the light of reported contemporary observations and audited data on transfusion rates, the assumption of a 5% event rate has been used to base the main sample size recalculation on.

The expected effect estimate can be derived from the literature. Our systematic review (1) and its most recent update has shown only one small trial published in 1998 (3), which randomised a total of 68 participants to either IOCS or standard care. The transfusion rate in the control group was 23.5% and 2.9% in the IOCS group. The control event rate is considerably higher than that observed in current UK practice and inconsistent with literature from other sources. It is likely to be due to a sample at exceptionally high risk of haemorrhage. Weaknesses that raise the risk of bias (e.g. inadequate concealment of randomisation) preclude reliance on it alone to inform our calculations. Non-obstetric literature evaluating IOCS in interventions with a moderate to high risk of transfusion has two high quality systematic reviews: a HTA report citing a RR of exposure to allogeneic blood of 0.59 (95% CI 0.48-0.73) with salvage (6); and a Cochrane review reporting a RR of 0.62 (95% CI 0.50-0.70) for transfusion with salvage compared with normal practice (7). Detecting smaller effect size is possible but the larger sample size required has to be balanced against the cost and practicability of undertaking such a trial. From the current best literature we assume an intervention effect at or around 0.6 (at a control event rate of 5%, the intervention group would have a transfusion rate of 3%).

We have discussed the issue of directionality of hypothesis and significance testing and provided a range of sample sizes in table 6. Figure 6 shows how the power of our 3050 sample changes across a range of control event rates (between 4-7%), experimental event rates (between 2-4%) and directionality of hypothesis (1- or 2-sided test).

Control event rate	Two sided test Power 80%	Two sided test Power 90%	One sided test Power 80%	One sided test Power 90%
7%	2116	2830	1666	2308
6%	2490	3332	1960	2714
5%	3012	4032	2374	3286
3%	5106	6836	4022	5570

The interim analysis of our pilot study has confirmed that primary outcome data can be obtained in virtually all the randomised women, since this information is collected at the end of the in-patient stay before hospital discharge. Our sample size allows for primary outcome data and follow up loss of around 1% (38) randomised cases.

